4.2.7.3 Sensitivity analysis

ORR, DCR, DoR and PFS will be re-analyzed at the time of the primary analysis using the investigator assessment of tumor response instead of ICR assessment, as sensitivity analyses.

ORR and exact 95% CI (Clopper Pearson) will be presented for the following:

- ORR by investigator assessment. The numerator (number of confirmed responses) will be based on RECIST as per investigator assessment and the denominator will be based on the full analysis set

- ORR for both confirmed and unconfirmed responses based on ICR assessment. The numerator will include unconfirmed responses in addition to confirmed responses and the denominator will be based on the EFR set.

Sensitivity analyses of PFS, DoR and DCR using the investigators assessment of RECIST will be performed in an analogous manner to those using the ICR described in Section 4.2.7.2 above.

In addition, ORR and BOR using the ICR will be summarised for the FAS.

For patients where measurable disease at baseline is not confirmed by the ICR and who therefore appear in the sensitivity analysis using FAS, but not the primary analysis set (evaluable for response), a detailed description of the reasons for being considered not evaluable will be described in the CSR.

A further comparison of each type of overall objective response (CR, PR, SD, PD, NE or without measurable disease at baseline) between investigator and ICR will be presented using the full analysis set. Details for the patients identified as responders by ICR and not by the investigator, as well as by the investigator and not by ICR will be given.

The concordance between response as assessed by ICR and by investigator with the full analysis set will be summarised by cross-tabulation of the number and percentage of patients with:

- Response declared by investigator and ICR
- Response declared by investigator but not ICR
- Response declared by ICR but not investigator
- No response declared by both investigator and ICR

The overall concordance rate will be calculated as the total number of agreements between investigator and ICR divided by the total sample size.

4.2.7.4 Subgroup analysis

The analyses of ORR, DCR, DoR, PFS at the time of the primary analyses and OS at the time of the final analysis will be repeated in the following subgroups of patients:

1. patients carrying a somatic deleterious or suspected deleterious variants in either of the *BRCA* genes (*BRCA1* or *BRCA2*) identified with current and potential future tumor based *BRCA* mutation assays
2. patients who don't carry a somatic deleterious or suspected deleterious variants in either of the *BRCA* genes (*BRCA1* or *BRCA2*) identified with current and potential future tumor based *BRCA* mutation assays

3. patients identified as having a deleterious or suspected deleterious variants in HRR-associated genes identified with current and potential future HRR gene mutation assays
4. patients identified as not having a deleterious or suspected deleterious variants in HRR-associated genes identified with current and potential future HRR gene mutation assays
5. Patients in either group 1 or 3, (if the number in group 1 or 3 separately is small [less than 10])
6. Patients not in group 1 or 3 (if the number in group 1 or 3 separately is small [less than 10])

If a subgroup has <10 patients then the subgroup will not be analyzed and a listing including response status will be produced instead.

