10. Confirmation of the availability of a formalin fixed, paraffin embedded (FFPE) tumor sample (or approximately unstained 20 sections mounted on glass slides prepared from the block) from the primary or recurrent cancer must be provided. All attempts should be made to provide the sample prior to first dose or soon thereafter. If archival tumor sample is not available, tumor sample from fresh biopsy is acceptable; however, any lesion biopsied during screening can no longer be selected as a target lesion.
11. Patients must have adequate organ and marrow function measured within 28 days prior to administration of IPs as defined below:
- Hemoglobin (Hb) ≥ 10.0 g/dL with no blood transfusion in the past 28 days
 - Absolute neutrophil count (ANC) $\geq 1.5 \times 10^9/L$
 - Platelet count $\geq 100 \times 10^9/L$
 - Total bilirubin $\leq 1.5 \times$ institutional upper limit of normal (ULN)
 - Aspartate aminotransferase (AST) (Serum Glutamic Oxaloacetic Transaminase [SGOT]) / Alanine aminotransferase (ALT) (Serum Glutamic Pyruvate Transaminase [SGPT]) $\leq 3 \times$ institutional upper limit of normal (ULN)
 - Creatinine clearance ≥ 50 mL/min
 - Urine protein:creatinine ratio (UPC) ≤ 1 OR proteinuria $\leq 2+$ on two consecutive dipsticks taken no less than 1 week apart. Patients with 2+ proteinuria on dipstick must also have UPC < 0.5 on 2 consecutive samples.
12. Adequately controlled blood pressure (systolic blood pressure [SBP] ≤ 140 mmHg; diastolic blood pressure [DBP] ≤ 90 mmHg) on maximum of 3 antihypertensive medications. Patients must have a blood pressure (BP) of $\leq 140/90$ mmHg taken in the clinic setting by a medical professional within 2 weeks prior to starting study. It is strongly recommended that patients who are on three antihypertensive medications be followed by a cardiologist or a primary care physician for management of BP while on study. Patients must be willing and able to check and record daily blood pressure readings.
13. Adequately controlled thyroid function, with no symptoms of thyroid dysfunction
14. Able to swallow and retain oral medications and without gastrointestinal (GI) illnesses that would preclude absorption of cediranib or olaparib.

15. Postmenopausal or evidence of non-childbearing status for women of childbearing potential as confirmed by a negative urine or serum pregnancy test within 7 days prior to start of IPs. Postmenopausal is defined as:
- Age \geq 60 years, or

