5.7.6 Withdrawal of Informed Consent for donated biological samples

If a patient withdraws consent to the use of donated biological samples, the samples will be disposed of/destroyed, and the action documented. If samples are already analyzed, AstraZeneca is not obliged to destroy the results of this research.

If the patient withdraws consent for the collection of the mandatory biological samples that are an integral part of the study (ie, the archival tumor sample or the mandatory biomarker blood samples), further study participation can be continued, if the patient is already receiving treatment with IPs.

The PI:

- Ensures patients' withdrawal of informed consent to the use of donated samples is notified immediately to AstraZeneca
- Ensures that biological samples from that patient, if stored at the study site, are immediately identified, disposed of /destroyed, and the action documented
- Ensures the laboratory(ies) holding the samples is/are informed about the withdrawn consent immediately and that samples are disposed of/destroyed, the action documented and the signed document returned to the study site
- Ensures that the patient and AstraZeneca are informed about the sample disposal.

AstraZeneca ensures the central laboratory(ies) holding the samples is/are informed about the withdrawn consent immediately and that samples are disposed of/destroyed and the action documented and returned to the study site.

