8.5.1 Analysis of the primary variable ORR

The primary analysis will be based on ICR assessments of tumor response. Only patients with a confirmed CR or PR, by ICR, at least 4 weeks after the initial response will be counted as responders.

The number of responders (confirmed CR or PR) will be modelled using a binomial distribution with a neutral Beta (1/3,1/3) prior distribution on the rate.

The mean and median of the posterior distribution of ORR will be presented, along with the standard deviation and a 95% credible interval around the mean (based on the highest posterior density [Lee, 1997]). The observed ORR by ICR will also be presented with 95% exact (Clopper Pearson) CIs.

The posterior probabilities of the ORR being larger than 15%, 20% and 24% will be also computed. To further characterize the RR, the posterior probability of showing low (<15%), moderate ($\geq 15\%$ - <20%), high ($\geq 20\%$ - <24%) or substantial ($\geq 24\%$) efficacy will be presented.

Summaries of the number of patients with best response in each of the follow categories will be presented: CR, PR, SD, PD and NE. For the interim analysis, the CR (PR) category will be split into confirmed CR (PR) and unconfirmed CR (PR).

At the time of primary analysis, ORR and exact 95% CI (Clopper Pearson) will be also be presented for the following:

- ORR by investigator assessment
- ORR for both confirmed and unconfirmed responses based on ICR assessment
- ORR based on ICR assessment in the subgroup of patients carrying a somatic deleterious or suspected deleterious variant in either of the *BRCA* genes (*BRCA1* or *BRCA2*) or in HRR-associated genes identified with current and potential future tumor based *BRCA* or HRR gene mutation assays (ICR and Investigator assessment)

The concordance between ORR (confirmed responses) as assessed by ICR and by Investigator will be presented.

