8.5.3 Subgroup analysis (if applicable)

The analyses of ORR, DCR, DoR, PFS and OS will be repeated for patients in and not in the following two subgroups:

- patients carrying a somatic deleterious or suspected deleterious variants in either of the *BRCA* genes (*BRCA1* or *BRCA2*) identified with current and potential future tumor based *BRCA* mutation assays
- patients identified as having a deleterious or suspected deleterious variants in HRR-associated genes identified with current and potential future HRR gene mutation assays.

Other subgroups may be analyzed, as detailed in the SAP.

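### The SAP produces the protocol's combined BRCA-or-HRR subgroup, and the only group negative for both, only when numbers are small, and it has no rule for patients without a tumor result

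*SAP*

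**What the plan says.** **Protocol, combined group.** The secondary objective in Section 2.2 takes BRCA and HRR variants together and covers ORR, DoR, DCR, PFS and OS. Section 8.5.1 schedules "ORR based on ICR assessment in the subgroup of patients carrying a somatic deleterious or suspected deleterious variant in either of the" BRCA genes or in HRR-associated genes. The synopsis has the same line. None of the three sets a minimum size.

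**Protocol, separate groups.** Section 8.5.3 lists a BRCA subgroup and an HRR subgroup, and says the analyses "will be repeated for patients in and not in the following two subgroups".

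**SAP.** Section 1.1.2 states the BRCA and HRR objectives separately. Section 4.2.7.4 defines six groups:
- Groups 1 and 3 are carriers of a somatic BRCA variant and of an HRR-gene variant.
- Group 2 is "patients who don't carry a somatic deleterious or suspected deleterious variants in either of the" BRCA genes.
- Group 4 is "patients identified as not having a deleterious or suspected deleterious variants in HRR-associated genes".
- Group 5 is "Patients in either group 1 or 3, (if the number in group 1 or 3 separately is small [less than 10".
- Group 6 is "Patients not in group 1 or 3 (if the number in group 1 or 3 separately is small [less than 10".

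Any subgroup with fewer than 10 patients is listed instead of analyzed. SAP Section 6, on changes from the protocol, has one entry, a quality-of-life threshold.

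**Tumor sample.** Inclusion criterion 10 requires that a sample be available and adds: "All attempts should be made to provide the sample prior to first dose or soon thereafter". Protocol Section 5.7.6 says that if a patient withdraws consent for the mandatory samples, "further study participation can be continued, if the patient is already receiving treatment with IPs".

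**The concern.** There are two separate problems.

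First, an analysis that the protocol plans unconditionally has become conditional in the SAP, and the change is not declared. The condition also works in an awkward direction. The combined group and its negative counterpart disappear when both mutated groups are large enough to analyze, which is when the contrast between any variant and none would be most informative.

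Second, neither document says where a treated patient with no sample, a failed assay or withdrawn sample consent belongs. The three negative groups in the SAP are worded in three different ways, so the programmer would have to choose.

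What is at stake is how activity in tumors with and without a repair-gene variant is described. It is a secondary objective, reported descriptively.

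**Working it through.** The plan gives no figure on this point to reproduce. Steps 1 and 4 compare text. Steps 2, 3 and 5 are illustrations with N = 60 (the planned size). The documents give no variant prevalence, untested share or subgroup ORR, so those inputs are assumptions.

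**Step 1. Combined group, side by side.**

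| Source | Combined group? | Size condition |
|---|---|---|
| Protocol 2.2, synopsis, 8.5.1 | Yes | None |
| Protocol 8.5.3 | No, two separate subgroups | None |
| SAP 1.1.2 | No, separate | None |
| SAP 4.2.7.4, groups 5 and 6 | Yes | Only if group 1 or 3 is under 10 |
| SAP 6 | Not mentioned | – |

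The conflict is therefore with Protocol 2.2, 8.5.1 and the synopsis. Section 8.5.3 agrees with the SAP's separate groups.

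**Step 2. How often the combined group would be dropped.** It is dropped when groups 1 and 3 both have at least 10 patients. With prevalence q, P(n ≥ 10) is the upper tail of Binomial(60, q). Treating the two counts as independent, the probability of dropping is the product of the two tails.

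| q, same for both | P(n ≥ 10) | P(dropped) | P(produced) |
|---|---|---|---|
| 10% | 0.073 | 0.073² = 0.005 | 0.995 |
| 15% | 0.412 | 0.412² = 0.17 | 0.83 |
| 20% | 0.787 | 0.787² = 0.62 | 0.38 |

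**Step 3. What remains when group 6 is dropped.** The HRR genes named in Protocol 1.4 and 5.7.2 and in SAP 1.2 do not include BRCA1 or BRCA2. So group 4 contains somatic-BRCA patients, and group 2 contains HRR-variant patients. Suppose groups 1 and 3 have 10 patients each without overlap, which leaves 40 with neither variant. Assume an ORR of 40% with a variant and 15% without.
- Group 4: 60 − 10 = 50 patients, ORR = (40 × 0.15 + 10 × 0.40)/50 = (6 + 4)/50 = 20%. Group 2 gives the same result by symmetry.
- Group 6, if it were produced: 40 × 0.15 = 6 of 40, or 15%.

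The 5-point gap equals the distance between the 15% and 20% efficacy cut-offs in SAP 4.2.7.1. Only group 6 shows the lower figure.

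**Step 4. Where a patient without a result falls.**
- Group 6 and the Protocol 8.5.3 wording are complements, so she counts as non-mutated.
- Group 4 requires her to have been identified as negative, so she is excluded.
- Group 2 can be read either way.

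The missing-value row in SAP 4.1 applies to count tables and does not assign patients to subgroups. Elsewhere the SAP does state evaluable denominators, for PROs (4.2.8) and for laboratory and vital-sign summaries (4.2.9).

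**Step 5. Size of the untested-patient effect.** Let u be untested patients (3 to 12, or 5% to 20% of 60) and m the carrier share, the same in tested and untested. A complement group then has (60 − u)(1 − m) + u patients, of whom u × m are hidden carriers. Its ORR is 0.15 + (0.40 − 0.15) × u × m / [(60 − u)(1 − m) + u].
- u = 3, m = 10%: 0.15 + 0.25 × 0.3/54.3 = 15.1%.
- u = 12, m = 30%: 0.15 + 0.25 × 3.6/45.6 = 17.0%.

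Untested patients would make up 3/54.3 = 5.5% to 12/45.6 = 26% of the complement group.

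**The case against.** **The objective is still analyzed.** If both mutated groups reach 10, groups 1 and 3 are each reported in full, as Protocol 8.5.3 and SAP 1.1.2 set out. This stands. A reader might infer that the subgroup objective would have no analysis at all, and the documents do not support that. What is lost is the pooled result that Protocol 2.2, 8.5.1 and the synopsis name, together with the doubly negative group.

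**Most SAP negative groups are not complements.** This also stands. A reader might infer from the Protocol 8.5.3 wording that every negative group in the SAP takes in untested patients. Only group 6 clearly does.

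**Tissue is mandatory.** Protocol 5.7.2 makes a patient ineligible without confirmed archival tissue or consent to a biopsy. A late sample is not a missing result, and Section 5.7.6 does not oblige the sponsor to destroy results already obtained. So untested patients are possible, but a reader who takes them as certain, or their number as known, goes beyond the documents. The baseline tables in SAP 4.2.3, with the missing row, should show how many there are. They do not say which subgroup those patients enter.

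**Group 4 is the proper counterpart of group 3.** It follows the protocol's in-and-not-in structure. A reader might infer from Step 3 that BRCA carriers must be removed from it. That is a preference, and it is unnecessary once group 6 is always produced.

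**The bias is small.** It is, set against a 95% interval of about ±10 points for 50 patients at 15% (1.96 × √(0.15 × 0.85/50) = 0.099).

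**Conclusion.** The point holds in two parts of unequal weight.

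The main part rests on the text alone. The SAP makes an unconditional protocol analysis conditional without declaring it, and when the condition fails no reported group is free of both variant types. How often that would happen depends on prevalence: from almost never at 10% each to about 0.62 at 20% each, assuming 60 tested patients and independent counts.

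The lesser part is the missing rule for unknown tumor status. As worded, group 6 and Protocol 8.5.3 put such patients with the non-mutated. On the assumed rates this shifts the ORR by about 0.1 to 2 points, and by nothing if every patient has a result.

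A reader might infer that misplaced untested patients could decide whether response is confined to repair-deficient tumors. The documents do not support that: these are single-arm descriptive repeats with no between-group test planned, and the shift is well inside sampling error.

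**What to change.** In SAP Section 4.2.7.4:
- Delete the size condition on groups 5 and 6, so that both are always formed. Keep the rule that a subgroup under 10 is listed and not analyzed.
- Define groups 2, 4 and 6 as patients with a valid tumor result showing no qualifying variant for that group. Apply the same definition to the not-in groups of Protocol Section 8.5.3.
- Report patients without a valid result as a separate unknown category, with their number.

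Group 4 can stay as the counterpart of group 3.

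If the sponsor prefers to keep the size condition, SAP Section 6 should list it as a departure from Protocol 2.2 and 8.5.1. That would declare the change but would not restore the planned analysis.

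The cost is one or two more descriptive tables and slightly smaller negative groups. No new data are needed.

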4.2.7.5 Exploratory endpoints

Biomarkers

The following biomarkers may be analyzed using plots and descriptive summary statistics.

- Biomarker of potential HRDs, including genomic scarring, *BRCAl* methylation, and other genes that might modify HRD.
- Biomarkers of gene expression signature for angioimmune/angio/immune/metabolic categorization
- Angiogenic biomarkers such as VEGF-A, C, D; sVEGFR2, Tie2, Ang1, 2; leptin; IL6

The exploratory biomarker analyses will be reported separately to the CSR.

4.2.8 PROs

Patients without a baseline PRO assessment will not be included in summaries of PRO endpoints.

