8.5.6 Exploratory analyses

The analyses of the exploratory endpoints will be further detailed in the SAP.

PRO-CTCAE

PRO-CTCAE data will be presented using summaries and descriptive statistics based on the FAS and further details will be provided in the SAP.

Biomarkers

The following biomarkers will be analyzed using plots and descriptive summary statistics.

- Biomarker of potential HRDs, including genomic scarring, *BRCA1* methylation, and other genes that might modify HRD.
- Biomarkers of gene expression signature for angioimmune/angio/immune/metabolic categorization
- Angiogenic biomarkers such as VEGF-A, C, D; sVEGFR2, Tie2, Ang1, 2; leptin; IL6

CA-125

Analysis of CA-125 samples will be described in the SAP.

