2.1.2 Efficacy analysis set (evaluable for response population [EFR])

The evaluable for response (EFR) analysis set will be all patients who have received at least one dose of treatment and have measurable disease at baseline according to the independent review of baseline imaging data.

The primary analysis of ORR, and analyses of DoR and DCR by ICR will be produced based on the EFR analysis set. All other efficacy variables (ORR, DoR, DCR based on investigator assessment; PFS [ICR and investigator assessment], OS, TDT) and PRO variables will be summarized using the FAS.

Demographic data will be summarized for the FAS and to support the primary analysis, also for the EFR set (if different).

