4.1.1 Baseline

Baseline will be the last assessment of the variable under consideration prior to the intake of the first dose of investigational product.

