4.1.3 Visit windows

The following conventions will apply:

- Listings should display all values contributing to a time point for a patient.
- For summaries at a patient level, all values should be included, regardless of whether they appear in a corresponding visit based summary, when deriving a patient level statistic such as a maximum.

- The time windows should be exhaustive so that data recorded at any timepoint has the potential to be summarised. Inclusion within the time window should be based on the actual date and not the intended date of the visit.

- All unscheduled visit data should have the potential to be included in the summaries.

- The window for the visits following baseline will be constructed in such a way that the upper limit of the interval falls half way between the two visits (the lower limit of the first post-baseline visit will be Day 2). If an even number of days exists between two consecutive visits then the upper limit will be taken as the midpoint value minus 1 day. For example, the visit windows for CA-125 data (with 8 weeks between scheduled assessments) are:
 - Day 57, visit window 2 – 84
 - Day 113, visit window 85 – 140
 - Day 169, visit window 141 – 196, etc

Data up to and including 30 days after last dose of either IP will be considered on treatment and presented by scheduled visit except for PRO data which will be reported as follow-up visit; thereafter data will be assigned to a post-treatment visit category.

- For summaries showing the maximum or minimum values, the maximum/minimum value recorded will be used (regardless of where it falls in an interval).
- For visit based summaries
 - If there is more than one value per patient within a time window then the closest value to the scheduled visit date should be summarised, or the earlier, in the event the values are equidistant from the nominal visit date. . Note: in summaries of extreme values all post baseline values collected are used including those collected at unscheduled visits regardless of whether or not the value is closest to the scheduled visit date
 - To prevent very large tables or plots being produced that contain many cells with meaningless data, for each treatment group, visit data should only be summarised if the number of observations is greater than the minimum of 20 and $> 1/3$ of patients dosed,

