4.2.8.1 PRO-CTCAE

Data from the PRO-CTCAE will be summarised for those patients with evaluable data. The number (%) of patients with each level of response for each PRO-CTCAE item at baseline and over time will be summarised.

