4.2.8.2 EORTC QLQ- C30 and EORTC QLQ- OV28

The EORTC-QLQ-C30 and EORTC-QLQ-OV28 questionnaires will be summarized. Descriptive statistics of absolute scores and change from baseline of all subscales will be presented and plots will be generated as appropriate to interpret changes over time.

Proportions of patients who had a best observed change of improved, stayed the same or deteriorated whilst on treatment (excluding follow-up) for all subscales (symptom and functioning scales) will be presented. A 10 point change in score will be used as cut-off point. Improved will be defined as the number (%) of patients with two assessments at least 18 days apart (i.e. 21 days allowing a visit window of 3 days) which showed a clinically meaningful improvement (a decrease from baseline score ≥ 10) in that symptom from baseline. The quantity and impact of missing data will be evaluated. If warranted, some investigation of HRQoL data by whether patients are still taking study drug will be performed.

Symptom Improvement Rate at 8 weeks

For dyspnea, pain and constipation from QLQ-C30 and abdominal/GI symptoms from QLQ-OV28, the symptom improvement rate at 8 weeks (follow-up data will be excluded) will be defined as the number (%) of patients showing a clinically meaningful improvement (a decrease from baseline score ≥ 10 ; Osoba et al 2005) in that symptom from baseline. The denominator will consist of a subset of the FAS population who have a baseline symptom score ≥ 10 . A 95% confidence interval for the symptom improvement rate will be constructed using the Clopper-Pearson method.

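### SAP 4.2.8, read literally, removes patients without a baseline PRO form from the PRO-CTCAE response-level tables, which need no baseline and which the protocol places on the FAS

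*SAP*

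**What the plan says.** The lead-in to SAP 4.2.8 reads: "Patients without a baseline PRO assessment will not be included in summaries of PRO endpoints". It names no instrument and no type of endpoint, and 4.2.8.1 (PRO-CTCAE) and 4.2.8.2 (EORTC QLQ-C30 and OV28) both sit beneath it.

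For PRO-CTCAE, SAP 4.2.8.1 gives a population: "Data from the PRO-CTCAE will be summarised for those patients with evaluable data". It also gives the output: "The number (%) of patients with each level of response for each PRO-CTCAE item at baseline and over time will be summarised".

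Elsewhere the set is the FAS. Protocol 8.5.6 states: "PRO-CTCAE data will be presented using summaries and descriptive statistics based on the FAS", and leaves further detail to the SAP. On PRO variables generally, SAP 2.1.2 states: "PRO variables will be summarized using the FAS"; Protocol 8.3.2 and SAP 1.2 agree. Membership of the FAS depends only on having taken a dose of either product (Protocol 8.3.1, SAP 2.1.1).

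SAP Section 6 declares one change from the protocol, the 10-point threshold for symptom improvement. It does not mention the baseline exclusion.

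**The concern.** A baseline form is needed to compute change from baseline, best observed change or the symptom improvement rate. It is not needed to count how many patients report each level of nausea or diarrhea at Week 4. Applied to that count, the rule leaves out valid on-treatment reports because of one absent form.

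PRO-CTCAE is in this study to record how patients themselves experience the combination; Protocol 5.3.1.2 justifies it by evidence that clinicians under-report symptoms. If patients without a baseline form differ from the rest, the tabulated frequencies are biased. If they do not differ, precision is lost. In either case a programmer has three population statements to reconcile and no rule for choosing between them.

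**Working it through.** The plan gives no figure on this point, so there is none to reproduce. The check sets the texts side by side and then sizes the loss under stated assumptions.

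**1. Which population applies to PRO-CTCAE levels?**

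| Source | Population | Baseline form required? |
|---|---|---|
| Protocol 8.5.6 | FAS | No |
| Protocol 8.3.2, SAP 1.2, SAP 2.1.2 (PRO variables) | FAS | No |
| SAP 4.2.8.1 | Patients with evaluable data | No |
| SAP 4.2.8 lead-in | Patients with a baseline PRO assessment | Yes |

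The lead-in alone asks for a baseline form. SAP 3.4, which defines an evaluable questionnaire for EORTC compliance, asks for a completion date and one non-missing subscale, again with no baseline condition. The lead-in also does not say whether the baseline form must be from the same instrument or whether any PRO form will do.

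**2. Which planned outputs need a baseline?**

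- PRO-CTCAE response levels by visit: no.
- EORTC absolute scores: no.
- EORTC change from baseline, best observed change, and symptom improvement rate at 8 weeks: yes.

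**3. Size.** Inputs: about 60 patients (Protocol 1.4); PRO-CTCAE on Day 1 and then weekly for 12 weeks (Protocol Table 5, SAP Table 8), taken as at most 12 post-baseline forms per patient by Week 12. Assumption, not in the documents: 5-15% of patients lack a baseline form.

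- Patients = 60 x rate: 60 x 0.05 = 3; 60 x 0.15 = 9.
- Forms by Week 12 = patients x 12: 3 x 12 = 36; 9 x 12 = 108.

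The form counts are ceilings, since they suppose that every affected patient stays on treatment for 12 weeks and completes every form. Forms after Week 12 would be additional.

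**4. Illustration of bias, with all rates assumed.** Suppose 10% are excluded, 40% of them report severe diarrhea, and 20% of the others do. The table shows 20%; all patients together would give 0.9 x 20% + 0.1 x 40% = 22%. With 54 patients in the table, the approximate 95% half-width around 20% is 1.96 x sqrt(0.20 x 0.80 / 54) = 0.107, or about 11 points. A shift of this size is small beside the sampling error.

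**The case against.** The strongest reply is that Protocol 8.5.6 hands further detail to the SAP, and that summarising on the FAS never means that every FAS patient enters every table. SAP 4.2.8.2 itself uses a subset of the FAS for the improvement rate, and SAP 4.2.9 limits laboratory and vital-sign denominators to patients with data. In addition, the population sentence in 4.2.8.1 is specific to PRO-CTCAE and could be read as overriding the lead-in. The first part stands as far as it goes: nobody expects a patient with no data at a visit to be counted there. But delegated detail does not explain leaving out patients who do have data, and it does not reconcile the lead-in with 4.2.8.1. If 4.2.8.1 was meant to govern, the SAP should say so.

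Three stronger readings are tempting, and the documents do not support them.

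- **That the rule will often be triggered.** Day 1 is the only scheduled pre-treatment PRO form, so a reader might infer that baselines are easily lost. Protocol 5.3.1.3 requires PROs before other procedures at a visit, and provides for reminders, compliance checks at each visit and a flag below 85%. No missing-baseline rate is given.
- **That a Day 1 form completed after dosing counts nowhere.** This might be inferred from SAP 4.1.1, "Baseline will be the last assessment of the variable under consideration prior to the intake of the first dose of investigational product", together with SAP 4.1.3, "the lower limit of the first post-baseline visit will be Day 2". But 4.1.3 also says that time windows should be exhaustive, so that data from any time can be summarised. Nor should such a form simply be accepted as baseline: that would contradict SAP 4.1.1 and Protocol 8.5.
- **That absolute EORTC scores must also be shown for all FAS patients with data.** SAP 4.2.8.2 plans: "Descriptive statistics of absolute scores and change from baseline of all subscales will be presented". The secondary objective is a comparison with baseline (Protocol 2.2, SAP 1.1.2), so keeping the same patients in both displays is defensible.

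**Conclusion.** The point holds for PRO-CTCAE. As written, the SAP 4.2.8 lead-in excludes patients from response-level tables that need no baseline, it conflicts with Protocol 8.5.6, SAP 2.1.2 and SAP 4.2.8.1, and Section 6 does not declare it. For the endpoints that use a baseline the rule is sound; the fault is its scope.

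The size is unknown. The range of 3-9 patients and at most 36-108 forms rests entirely on an assumed 5-15% without a baseline form. The direction and amount of any bias depend on whether those patients differ from the rest, on which the documents are silent.

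The consequence is limited. PRO-CTCAE is exploratory and descriptive (Protocol 2.4), and the primary ORR analysis is untouched. The reports would be left out of summary tables, not deleted. Clinician-reported adverse events are tabulated separately, with grade changes recorded for diarrhea, fatigue and nausea (SAP 3.3.3) and plotted by patient (SAP 4.2.9). For HRQoL, SAP 4.2.8.2 also commits to evaluating missing data. The correction is worth making because it is specific, cheap and removes a contradiction.

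**What to change.** Replace the lead-in sentence of SAP 4.2.8 with wording to this effect: patients without a baseline assessment on the relevant instrument are excluded only from endpoints that use a baseline, namely change from baseline, best observed change and the symptom improvement rate; PRO-CTCAE response levels at each visit are summarised for all FAS patients with an evaluable form at that visit; and the number of patients without a baseline form is reported for each instrument.

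State also which patients enter the absolute QLQ-C30 and OV28 summaries. Using all FAS patients with data is optional; keeping the change-score patients is acceptable if stated. The definition of baseline stays as it is.

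The cost is about two sentences in the SAP, with no new data. The one small downside is that patient numbers at a visit may differ slightly between tables, which a footnote can explain. If the sponsor prefers to keep the exclusion for PRO-CTCAE, it should be declared in SAP Section 6 with a reason, and SAP 2.1.2 and 4.2.8.1 should be brought into line.
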